12.4	Screening Criteria - Excluded Medications	84

List of Tables

Table 1: Schedule of Events.....	20
Table 2 Assumed Proportions for Wilcoxon Rank Sum Test of Vaginal Dryness	57
Table 3: Gatekeeping Procedure for Efficacy Analyses.....	60

List of Figures

Figure 1: Estriol Structural Formula	30
--	----

Protocol Synopsis

Protocol Number:	ITFE-2092-C1
Title:	A Phase 2, Dose-ranging, 12-week, Randomized, Double-blind, Placebo-controlled, Parallel-group Study Evaluating the Efficacy and Safety of Three Formulations of Ultra-low Dose Estriol Vaginal Gel (0.005% Estriol Vaginal Gel, 0.002% Estriol Vaginal Gel, 0.0008% Estriol Vaginal Gel) for the Treatment of Vaginal Dryness in Postmenopausal Women with Vulvovaginal Atrophy
Sponsor:	ITF Research Pharma SLU [name] [name]
Study Phase:	Phase 2
Study Sites:	Approximately 25, in 5 European countries (Spain, Italy, Sweden, Hungary, Czech Republic).
Indication:	Treatment of vaginal dryness in postmenopausal women with vulvovaginal atrophy
Rationale:	Local estrogen therapy is the recommended approach to treat symptoms related to postmenopausal vulvovaginal atrophy. An estriol-based formulation allowing a lower dose per application provides reduced estrogen exposure while maintaining efficacy, resulting in fewer systemic effects and a more favorable risk-benefit ratio for the patient.
Objectives:	
Primary objective: Evaluate the efficacy of 0.005%, 0.002%, and 0.0008% estriol vaginal gel and determine the minimal effective dose for the treatment of postmenopausal vaginal atrophy in women who report moderate to severe vaginal dryness as the most bothersome symptom.
 
Secondary objectives: Evaluate the efficacy of the three formulations of estriol vaginal gel in the improvement of other symptoms and signs of vulvovaginal atrophy.
 
Evaluate the safety and tolerability of the three formulations of estriol vaginal gel.
 
Exploratory objectives: Evaluate the final subjective global perception of efficacy of the three formulations of estriol vaginal gel.
 
Evaluate the subject's acceptability of the three formulations.

Subject Population:

Inclusion criteria:

1. Capable of understanding the written informed consent, provides signed and witnessed written informed consent, and agrees to comply with the protocol procedures and assessments
2. Age ≥ 40 and ≤ 80 years
3. Postmenopausal (≥ 12 months since last spontaneous menstrual period, or having 6 months of spontaneous amenorrhea with serum FSH levels >40 IU/L, or ≥ 6 weeks since bilateral oophorectomy with or without hysterectomy)
4. BMI ≤ 36 kg/m²
5. Vaginal Maturation Index $\leq 5\%$ superficial cells on a vaginal smear
6. Vaginal pH >5
7. Moderate to severe vaginal dryness currently reported as the most bothersome symptom of vaginal atrophy.
8. Negative mammogram at screening or documented negative mammogram within 9 months prior to randomization, with normal breast examination at screening.
9. Negative Papanicolaou test at screening (in women with cervix).

Exclusion criteria:

1. Subjects with contraindications for hormone therapy with estrogens such as those diagnosed or history of: malignant and premalignant lesions of the breast and/or endometrium, malignancy of the colon, malignant melanoma, hepatic tumor, venous thromboembolic conditions (including deep vein thrombosis or pulmonary embolism), arterial thromboembolic conditions (including angina pectoris, myocardial infarction, or cerebrovascular accident), coagulopathies, vaginal bleeding of unknown etiology, acute liver disease or a history of liver disease as long as liver function tests have failed to return to normal, or porphyria.
2. Subjects who have abnormal laboratory values at screening that the investigator considers clinically relevant for the purposes of the study.
3. Subjects with any medical-surgical pathology which is not controlled at the time of inclusion in the study.

Subject Population:

Exclusion criteria (continued):

4. Subjects with any acute or chronic condition whose management or progression may interfere with the subject's participation in the study.
5. Subject with uncontrolled hypertension (≥ 140 mmHg systolic blood pressure and/or ≥ 90 mmHg diastolic blood pressure).
6. Subjects with Grade II or higher utero-vaginal prolapse.
7. Subjects with uterine polyps.
8. Subjects with symptomatic and/or large uterine fibroids (>3 cm) and/or palpable fibroids at gynecological examination.
9. Subjects who have had urogenital surgery within 3 months of baseline visit.
10. Subjects with signs and symptoms suggestive of infection of the genital or urinary tract requiring treatment at the start of the study.
11. In women who have a uterus, evidence of hyperplasia, cancer or other endometrial pathology in endometrial biopsy.
12. Subjects who have received the following treatments within the specified time periods prior to screening procedures: any type of non-hormonal vulvovaginal treatment in the 7 days (including cosmetics expected to have an impact on vaginal pH such as special feminine wash gels); phytoestrogens by any route within 1 month; vaginal hormone therapy within 1 month; hormone therapy (estrogen alone, progestin alone or estrogen/progestin combination) by oral, intrauterine or transdermal route within 2 months; progestational implants, estrogen, or estrogen/progestational injectable within 3 months; estrogen pellet therapy or progestin injectable drug therapy within 6 months; percutaneous estrogen lotions or gels within 1 month; testosterone or testosterone derivatives, DHEA, tibolone, or SERMs by any route within 2 months;
13. Subjects receiving antiepileptic drugs (barbiturates, hydantoins, carbamazepine), certain antibiotics and other antiinfective medicinal products; phenylbutazone; preparations based on medicinal plants that contain St. John's Wort.

Subject Population:

Exclusion criteria (continued):

14. Subjects who are allergic to any of the components of the medication under study.
15. Subjects who are currently participating or have participated in the experimental evaluation of any product within 8 weeks of the start of the study.

Study Design:

Dose-ranging, 12-week, multicenter, randomized, double-blind, placebo-controlled, parallel-group study.

Estimated Study Duration:

Study duration will be approximately 20 weeks from the Screening Visit to End-of-Study phone call. Subject exposure to study drug will last 12 weeks, with a total of up to 6 study visits (including one telephone call visit).

Efficacy Assessments:

The co-primary efficacy variables in this study are:

- Mean change from Baseline to Week 12 in the proportion of superficial and parabasal cells of the vaginal epithelium on vaginal smear;
- Mean change from Baseline to Week 12 in vaginal pH;
- Mean change from Baseline to Week 12 in the severity of vaginal dryness

The secondary efficacy variables:

- Mean change from Baseline to Week 3 in the proportion of superficial and parabasal cells of the vaginal epithelium;
- Mean change from Baseline to Week 3 in vaginal pH;
- Mean change from Baseline to Week 3 in the severity of vaginal dryness
- Mean change of other individual vaginal symptoms (dyspareunia, pruritus, burning and dysuria) and signs (pallor, friability, thinning or flattening of folds, petechiae, and dry mucosa) of vaginal atrophy from Baseline to Week 3 and from Baseline to Week 12
- Mean change in the Global Symptom Score from Baseline to Week 3 and from Baseline to Week 12

The exploratory efficacy variables:

- Evaluation of the final subjective global perception of efficacy by subjects at Week 12.
- Evaluation of the acceptability of the therapy at Week 12.

Safety Assessments:

The safety variables in this study are:

- Evaluation of adverse events
- Histological evaluation of the endometrium by endometrial biopsy
- Evaluation of the endometrium by ultrasonography
- Change in hormone levels
- Change in clinical safety laboratory parameters
- Safety assessments of lipids and of carbohydrate and coagulation parameters (antithrombin III, factor V Leiden, protein-C and protein-S)

Study Drug, Dosage, and Route of Administration:

0.005% estriol vaginal gel, 1 g (50 µg estriol/intravaginal application dose), 0.002% estriol vaginal gel, 1 g (20 µg estriol/intravaginal application dose), 0.0008% estriol vaginal gel, 1 g (8 µg estriol/intravaginal application dose), placebo vaginal gel, 1 g (intravaginal administration)

Sample Size:

A total of 280 subjects randomly assigned equally to 0.005% estriol vaginal gel, 0.002% estriol vaginal gel, 0.0008% estriol vaginal gel, or placebo.

Statistical Methods:

The Intent-to-Treat (ITT) Population, the Per Protocol (PP) Population, and the Safety Population will be used to present the results.

Changes from Baseline to Week 12 in vaginal dryness will be analyzed using a Wilcoxon Rank Sum test, controlled for country, to obtain the p-values. The changes from Baseline to Week 12 in vaginal pH and the changes in proportions of parabasal and superficial cells will be analyzed using a parametric ANCOVA. The model will include fixed effects of treatment and country, and the baseline value will be used as a covariate. Model assumptions will be examined and, if required, a Wilcoxon Rank Sum test as described for vaginal dryness will be used. Missing values will be estimated using last observation carried forward (LOCF). Only post-Baseline values will be carried forward.

For the co-primary endpoints (change from Baseline to Week 12 in proportion of superficial and parabasal cells of the vaginal epithelium, pH, vaginal dryness), a gatekeeping procedure will be employed. 0.005% dose will be compared to placebo, and if this is significant at a one-sided alpha level of 0.025 then the other doses versus placebo can be considered in order of strength (strongest first); if all four co-primary endpoints are significant at the one-sided 2.5% level, then the next lowest dose can be presented; this approach will avoid any issues of multiple testing with four co-primary endpoints and three comparisons.

The change from Baseline to Week 12 in the severity of individual vaginal symptoms (dyspareunia, dryness, pruritus, burning and dysuria) and signs (pallor, friability, thinning, petechiae, flattening of folds and dry mucosa) will be assessed using the same Wilcoxon Rank Sum test as for the co-primary endpoint of vaginal dryness at Week 12. The change from Baseline to Week 12 in the global symptom score will be assessed using the same parametric ANCOVA as for the co-primary endpoints of vaginal pH and proportions of parabasal and superficial cells at Week 12. The Week 3 efficacy endpoints will be assessed using similar methodology as Week 12.

Endpoints of acceptability of therapy, final subjective global perception, and safety analyses will be summarized by treatment group.

Date of Protocol:

07 June 2017

List of Abbreviations

Abbreviation	Definition
AE	adverse event
ANCOVA	analysis of covariance
BMI	body mass index
CFR	Code of Federal Regulations
CRO	contract research organization
CSA	clinical study agreement
E1	estrone
E2	17 β -estradiol
E3	estriol
ECG	electrocardiogram
eCRF	electronic case report form
ER	estrogen receptor
FDA	US Food and Drug Administration
FSH	follicle-stimulating hormone
GCP	Good Clinical Practice
GI	Gastrointestinal
ICF	informed consent form
ICH	International Conference on Harmonisation
IEC	independent ethics committee
IRB	institutional review board
ITT	intention to treat
IWRS	Interactive Web Response System
LH	luteinizing hormone
LOCF	Last observation carried forward
MedDRA	Medical Dictionary for Regulatory Activities
OTC	over-the-counter
PP	per protocol
PV	pharmacovigilance
SAE	serious adverse event
SAP	statistical analysis plan
SERM	selective estrogen receptor modulator
SOC	system organ class
SUSAR	suspected unexpected serious adverse reaction
TVU	transvaginal ultrasound

1 Introduction

Vulvovaginal atrophy is a natural consequence of the progressive estrogen deficiency that occurs in menopause. Epidemiological data have indicated that about 50% of otherwise healthy women over 60 years of age experience symptoms related to urogenital atrophy such as vaginal dryness, dyspareunia, burning, itching, as well as urinary complaints or infections of the lower urinary tract. As these alterations frequently affect the quality of life of postmenopausal women, it is important for doctors to detect their presence and offer treatment options.

Estrogen therapy is the most effective treatment of moderate to severe symptoms of vulvar and vaginal atrophy. Scientific societies agree that when estrogen therapy is considered for treatment of vaginal atrophy, local treatment is advised (The 2007 Hormone Therapy Position Statement of the North American Menopause Society, 2007). One advantage of local treatment with estrogen is avoidance of first-pass liver metabolism, making it possible to use lower doses of estrogen compared with oral therapy; the local route also minimize systemic adverse effects.

The primary risks of taking an estrogen product after menopause is that it can cause or exacerbate certain types of tumors, such as breast or endometrium. Taking low dose estrogens vaginally decreases the risk of the occurrence of these tumors, as a consequence of the very low doses employed that permit a local vaginal effect while the potential of absorption is minimized. It has been shown that lower doses of vaginal estrogen therapy than previously used, even with less frequent administration, often yield satisfactory results. The lowest effective dose of estrogen consistent with treatment goals, benefits, and risks for the individual woman should be the therapeutic goal (The 2012 Hormone Therapy Position Statement of the North American Menopause Society, 2012).

Estriol (E3) is one of the most important estrogens produced in the human body, along with 17β -estradiol (E2) and estrone (E1). Estriol is normally produced in the liver by irreversible transformation of estradiol and estrone. This process is considered to be a metabolic detoxification mechanism, by which potent estrogens are transformed into less active metabolites such as estriol. Also, estriol is produced in significant amounts during pregnancy as it is synthesized by the placenta. In all instances, there is no conversion from estriol to estradiol or estrone.

The physiological effect of estrogens is complex: they exert their action through the activation of specific nuclear receptors, and different estrogens bind with different affinities to their receptors. Two subtypes of estrogen receptors (ERs) have been identified; these subtypes are ER α and ER β , with different tissue distributions, although there is some overlap in their expression, as ER α is most abundantly expressed in the endometrium, breast, and ovarian stroma. The relative binding affinities of different estrogens for their receptors has been investigated in different models against 17 β -estradiol, the most potent natural estrogen. In this sense, the binding affinities of estriol to ER α and ER β have been shown to be 14% and 21% of those of estradiol, respectively (Gruber CJ, 2002). Also, the differential expression of receptors in tissues results in topological (tissue) differences in the affinities of the various estrogens. Compared to estradiol, estriol shows a relatively high affinity for the receptors in bladder and vaginal tissue, but relatively low affinity for receptors in the uterine and breast tissue (Bergink EW, 1984). The lower affinity in the uterus results in minimal or no uterotrophic influence with estriol exposure (Takahi K, 2000) (Raz R, 1993) (Padwick ML, 1986) (Reynolds TM, 1993). The non-uterotrophic effect is also attributed, in part, to its relatively short duration of nuclear receptor binding and rapid plasma clearance (Cardozo L, 1998) (van Haaften M, 1997).

Other claimed advantages of estriol over other natural estrogens include a protective effect against development of breast cancer, minimal mitogenic activity, less effect on plasma lipids and coagulation factors/platelets, and an ability to reduce/block the uterotrophic activity of other estrogens (competition with receptor binding) (Takahi K, 2000) (Padwick ML, 1986) (Hayashi T, 2000) (Nakayama H, 1999).

Estriol formulations have been marketed since 1958 for the treatment of vulvovaginal atrophy in more than 50 countries worldwide, including all European countries, but not the United States. Topical (vaginal) formulations are currently available as creams (containing 1 mg estriol/1 g cream) or as ovules (containing 0.5 mg estriol). Local vaginal estrogen therapy can also be administered in the form of estradiol vaginal tablets or vaginal creams, estradiol-releasing vaginal rings and conjugated estrogen-based vaginal creams.

The search for therapeutic alternatives which may present improvements in relation to the current products has been encouraged. I [REDACTED]

[REDACTED]

[REDACTED]

[REDACTED]

[REDACTED]

Clinical research to develop this product was performed in European populations under European guidelines. [REDACTED]

2 Study Objectives

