4.1.1 Inclusion Criteria

Each subject must meet all of the following criteria to be enrolled in this study:

1. Is capable of understanding the written informed consent, provides signed and witnessed written informed consent, and agrees to comply with protocol procedures and assessments.
2. Is ≥ 40 and ≤ 80 years old.
3. Is postmenopausal, defined as ≥ 12 months since last spontaneous menstrual period, or having 6 months of spontaneous amenorrhea with serum follicle-stimulating hormone (FSH) level >40 IU/L, or ≥ 6 weeks since bilateral oophorectomy with or without hysterectomy.
4. Has a body mass index (BMI) ≤ 36 kg/m².
5. Vaginal Maturation Index showed $\leq 5\%$ superficial cells on a vaginal smear.
6. Vaginal pH is >5 .
7. Moderate to severe vaginal dryness is currently reported as the most bothersome symptom of vaginal atrophy.
8. Negative mammogram at screening or documented negative mammogram within 9 months prior to randomization and normal breast examination at screening.
9. Negative Papanicolaou test at screening (in women with a cervix).

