7.5 Sample Size Calculations

A total of 280 female subjects will be enrolled in the study.

The estimates of treatment differences and variability were gained from the results of Study ITFE-2026-C2.

A sample size of 57 in each group will have 90% power to detect a treatment difference for change in severity of vaginal dryness, assuming 5 categories with proportions in each treatment group as shown in the table below, using a Wilcoxon rank sum test with a 0.025 one-sided significance level.

Table 2 Assumed Proportions for Wilcoxon Rank Sum Test of Vaginal Dryness

Change in Vaginal Dryness Severity	Proportion in Estriol Vaginal Gel Group	Proportion in Placebo Group
-3	0.189	0.118
-2	0.423	0.196
-1	0.270	0.353
0	0.118	0.333
1	0	0

A sample size of 48 in each group will have 90% power to detect a treatment difference of -0.89 for change in vaginal pH, assuming a common standard deviation of 1.33 using a two-group t-test with a 0.025 one-sided significance level.

A sample size of 24 in each group will have 90% power to detect a treatment difference of 21 for change in proportion of superficial cells, assuming a standard deviation of 26.3 for 0.005% estriol vaginal gel and 14.8 for placebo vaginal gel, using a two-group Satterthwaite t-test with a 0.025 one-sided significance level.

A sample size of 9 in each group will have 90% power to detect a treatment difference of -53 for change in proportion of parabasal cells, assuming a standard deviation of 37.9 for 0.005% estriol vaginal gel and 19.6 for placebo vaginal gel, using a two-group Satterthwaite t-test with a 0.025 one-sided significance level.

The largest sample size calculated for a single co-primary endpoint has been considered the sample size required for the whole study, thus, 57 subjects per group are estimated. Accounting for an 18% drop-out rate, and rounding numbers, approximately 70 subjects/group have been finally estimated.

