The proportion of superficial cells will be summarized using descriptive statistics for continuous variables by treatment and visit in a general summary table of vaginal cytology parameters. The change from Baseline (Screening) value will also be summarized for all post-Baseline visits.

The mean change in proportion of superficial cells from Baseline to the Week 12 / Early Termination visit will be analyzed using a parametric analysis of covariance (ANCOVA) model. The model will include treatment and country as fixed effects and the Baseline (Screening) proportion of superficial cells will be used as a covariate. The adjusted (least-square) mean (LS Mean) change in proportion of superficial cells from Baseline to Week 12 will be presented for each treatment, along with the corresponding SE. The difference in LS Means between treatment groups (0.005% Estriol versus Placebo, 0.002% Estriol versus Placebo and 0.0008% Estriol versus Placebo) will also be presented with 95% CI and one-sided p-value. The p-values for the model parameters of country and Baseline proportion of superficial cells will also be presented. Model assumptions will be examined and, if required, a Wilcoxon Rank Sum test as described for vaginal dryness (Section 6.3.1.1) will be used. Missing values at Week 12 will be estimated using LOCF methodology for the ITT population analysis only. Only post-Baseline values will be carried forward.

6.3.1.4 Change from Baseline to Week 12 in Proportion of Parabasal Cells of the Vaginal Epithelium

The proportion of parabasal cells is based on the evaluation of vaginal smears by two pathologists at [REDACTED] and the change from Baseline to Week 12 will be summarized and analyzed exactly as described for superficial cells in Section 6.3.1.3.

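### The superficial-cell ANCOVA's only patient-level covariate is held to 0–5% by inclusion 5; baseline parabasal share could be added as an optional, nearly free gain in precision

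*Protocol*

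**What the plan says.** Protocol 4.1.1, criterion 5, admits women with at most 5% "superficial cells on a vaginal smear". For vaginal pH and both cell proportions, the Synopsis (Statistical Methods) and Protocol 7.8.1 specify one form of ANCOVA: "The model will include fixed effects of treatment and country, and the baseline value will be used as a covariate". SAP 6.3.1.3 applies it to superficial cells: "the Baseline (Screening) proportion of superficial cells will be used as a covariate". Week 3 (SAP 6.3.2.25) refers back to that model. The MMRM in SAP 6.3.1.6 adjusts for country and the endpoint's own baseline.

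Protocol 6.2.1 has parabasal, intermediate and superficial cells counted on the same smear. The baseline parabasal share enters only the parabasal model (SAP 6.3.1.4).

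Protocol 7.5 sizes superficial cells without any covariate: "A sample size of 24 in each group will have 90% power to detect a treatment difference of 21". The SDs of change behind that figure are 26.3 on the 0.005% gel and 14.8 on placebo, and the test is an unequal-variance (Satterthwaite) t-test at one-sided 0.025. For parabasal cells the planned difference is −53 points, and the sizing again lets the SDs differ by arm: "assuming a standard deviation of 37.9 for 0.005% estriol vaginal gel and 19.6 for placebo vaginal gel". No separate effect is stated for 0.002% or 0.0008%.

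**The concern.** Adjusting for an endpoint's own baseline normally buys precision because the baseline varies between women and predicts the outcome. Here the entry rule that selects the women also compresses the covariate into a 5-point band, so the adjusted analysis is likely to be close to the unadjusted one. Among women who all have 0–5% superficial cells, the split between parabasal and intermediate cells is the smear information that can still separate degrees of atrophy, and the model for this endpoint does not use it.

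Precision on one co-primary endpoint is what is at stake. It matters most at 0.002% and 0.0008%, where effects may be smaller and where superficial cells, like the other three endpoints, must reach significance before a dose counts as effective (Protocol 7.8.1.1).

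**Working it through.** **Inputs from the documents.** SD of change in superficial cells 26.3 (0.005% gel) and 14.8 (placebo); difference 21; one-sided alpha 0.025; 57 per arm before drop-out (Protocol 7.5). Baseline superficial cells 0–5% (Protocol 4.1.1).

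**Assumed, because the documents do not give them.** The slope of change on baseline superficial cells; the partial correlation r between baseline parabasal share and superficial-cell change; the effects and SDs at the lower doses.

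**1. The plan's own figure.** Satterthwaite t-test power from the noncentral t, with SE = sqrt((26.3² + 14.8²)/n). At n = 24, SE = 6.16 and power is 91.3%; the smallest n reaching 90% is 23. The stated 24 is reproduced within rounding. At 57 per arm, SE = 4.00 and power for 21 points is 99.9%.

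**2. What the planned covariate can explain.** A variable confined to 0–5 has an SD of at most 5/2 = 2.5 points, and about 1.4 if uniform. Share of variance explained = (slope × SD of baseline / SD of change)². Average variance = (26.3² + 14.8²)/2 = 455.4. The table takes the largest possible baseline SD, 2.5.

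| Slope magnitude | 0.005% arm | Placebo | On average variance | Fall in SE |
|---|---|---|---|---|
| 1 | 6.25/691.7 = 0.9% | 6.25/219.0 = 2.9% | 6.25/455.4 = 1.4% | 0.7% |
| 2 | 25/691.7 = 3.6% | 25/219.0 = 11.4% | 25/455.4 = 5.5% | 2.8% |

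At a baseline SD of 1.5 the average figures are 0.5% (slope 1) and 2.0% (slope 2).

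**3. What a parabasal covariate could add.** SE is multiplied by sqrt(1 − r²), which is equivalent to 1/(1 − r²) times as many women. Power is for an assumed lower-dose effect of 10.5 points (half of 21) at 57 per arm, with placebo SD 14.8. The lower-dose SD is set either at the full-dose 26.3 or midway, (26.3 + 14.8)/2, about 20.6.

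| r | Fall in SE | Equivalent extra women | Power, SD 26.3 | Power, SD 20.6 |
|---|---|---|---|---|
| 0 | 0% | 0% | 74% | 87% |
| 0.2 | 2% | 4% | 76% | 88% |
| 0.3 | 5% | 10% | 78% | 90% |
| 0.5 | 13% | 33% | 85% | 95% |

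**4. Effect on the gate.** Halve every effect in Protocol 7.5 at 57 per arm, keeping the planned SDs: dryness proportions midway to placebo, pH −0.445, superficial 10.5, parabasal −26.5. Power is then about 36% for dryness, 43% for pH, 74% for superficial cells and above 99% for parabasal cells. If the endpoints were independent, the chance of passing all four is 0.36 × 0.43 × 0.74 × 0.996, about 11%, and it rises to about 13% at r = 0.5. If they were strongly dependent, dryness would cap it near 36% with or without the added covariate.

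**5. Is the parabasal baseline widely spread?** Criterion 5 sets no direct limit on it. A difference of −53 implies a mean baseline of at least 53% on active gel, unless placebo worsens. Together with an SD of change of 37.9 this is consistent with a wide baseline spread. It does not measure it, because the SD of change also contains variation in response.

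**The case against.** The strongest reply is that nothing here is wrong. The model is pre-specified consistently, the randomised comparison is unbiased, alpha is unaffected, and no stated sample size relies on covariate gain. All of that stands.

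The benefit is also assumed. The documents give neither the spread of baseline parabasal share nor its correlation with superficial-cell change, and r = 0 is possible. Nor does a narrow range alone prove a covariate useless: correlation does not depend on scale, a steep slope would raise the variance explained, and women randomised in breach of criterion 5 could widen the range in the ITT set. These points stand too. They are why the claim is only that the covariate is likely to explain little, and why slope 2 and r = 0 are shown.

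The power illustration is pessimistic if the SD falls with the effect, as the planned SDs of 26.3 and 14.8 suggest it may; hence the column at 20.6.

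A reader might infer that chance imbalance in baseline atrophy would bias this endpoint. The documents do not support that. Chance imbalance is already reflected in the standard error, and it shifts the estimate only if the covariate is prognostic. With r = 0.3, an assumed baseline SD of 34 and a change SD of sqrt(455.4) = 21.3, a 10-point parabasal imbalance moves the estimate by 10 × 0.3 × 21.3/34, about 1.9 points, against 21 planned.

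Finally, if the ANCOVA assumptions fail, the plan moves to a country-controlled Wilcoxon test, which has no baseline covariate, and the added term would then do nothing.

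Against all this, the data are already collected and the cost is negligible, so the suggestion survives as an option.

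**Conclusion.** The point holds as a modest, optional gain in precision on one endpoint. Apart from country, a fixed effect, the superficial-cell model adjusts only for a value with an SD of at most 2.5 points. That value is likely to explain at most about 1.4% of average variance at a slope of magnitude 1, or about 5.5% at slope 2. Adding baseline parabasal share would lower the standard error by 0% to 13% for r between 0 and 0.5; where r lies in that range cannot be told from the documents.

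Two stronger readings are tempting and not supported. One is that the planned analysis is defective: it is valid, and power at 0.005% is already above 99%. The other is that the change would materially help a lower dose through the gate: with all effects halved, dryness and pH are the weaker endpoints, and the all-four probability moves only from about 11% to 13% even at r = 0.5. What remains is better precision for superficial cells at 0.002% and 0.0008% if their effects are smaller than planned for 0.005%.

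**What to change.** Before unblinding, add the Baseline (Screening) proportion of parabasal cells as a second covariate, beside baseline superficial cells, in SAP 6.3.1.3. Do the same in the Week 3 analysis (6.3.2.25) and the superficial-cell MMRM (6.3.1.6). Record in SAP 6.8 that the reason is the entry limit in criterion 5. The parabasal model stays as it is. The sponsor could first check the correlation in Study ITFE-2026-C2, the source of its variability estimates. If the sponsor prefers the current model, one sentence saying why is enough.

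The cost is one model term and one degree of freedom. No new data are needed, since both proportions are read from the same smear.
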